12.1.1 Missing Data

The amount and nature of missing data will be characterized and no method of imputation will be used for missing data. A summary of missing data will be provided according to the number of subjects, the time points where the data are missing, and clinical center. For each clinical center, the number and percent of subjects with no missing data will be presented in tabular form

All analyses will be performed using the SAS® statistical software system.

12.2 Study Objectives

The primary objective of this study is:

• To evaluate 6 month progression-free survival (PFS) rates in patients with survivin positive newly diagnosed GBM treated with SurVaxM and adjuvant temozolomide.

The secondary objectives of this study are:

- To determine the safety and tolerability of SurVaxM in patients receiving standard of care temozolomide.
- To evaluate overall survival (OS) in patients with survivin positive newly diagnosed GBM treated with SurVaxM and adjuvant temozolomide.
- To describe the immune response in patients treated with SurVaxM and predictors of response.
- To evaluate objective tumor response rate (applicable only for patients with evaluable disease at study entry, as defined per RANO criteria) and predictors of response.

12.3 Study Endpoints

Primary Endpoint:

• PFS is defined as the time from date of diagnosis to the date of first observed disease progression or death due to any cause. All patients will be followed for a minimum of 6 months relative to evaluating the primary endpoint.

Secondary Endpoints:

- OS is defined as the time from date of diagnosis until date of death or the last date patient known alive (if death is not observed).
- Number of Grade 3 or 4 toxicities, according to National Cancer Institute Common Toxicity Criteria for Adverse Events (NCI CTCAEs) Version 4
- Immune responses to SurVaxM and predictors of response

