10.1.3 Reporting Adverse Events

Table 4 Guidelines for Routine Adverse Event Reporting for Phase 2 Studies (Regardless of Expectedness)

Attribution	Grade 1	Grade 2	Grade 3	Grade 4
Unrelated			X	X
Unlikely			X	X
Possible	X	X	X	X
Probable	X	X	X	X
Definite	X	X	X	X

Routine AEs occurring between the start date of intervention until 30 days after the last intervention or until the event has resolved, the study participant is lost to follow-up, the start of a new treatment, or until the study investigator assesses the event(s) as stable or irreversible, will be reported. New information will be reported after it is received.

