Both objective tumor response rate (applicable only for patients with evaluable disease at study entry, as defined per RANO criteria) and toxicity rate (Grade 3 or Grade 4 toxicities, according to National Cancer Institute Common Toxicity Criteria for Adverse Events (NCI CTCAEs) Version 4) will be estimated using simple relative frequencies. The corresponding 95% confidence intervals for the estimated probabilities will be computed using the method proposed in Clopper and Pearson, 1934 ⁽⁴³⁾. The relationship between binary outcomes and collected demographic and baseline variables will be statistically assessed using logistic regression in an exploratory fashion. Maximum likelihood estimation will be utilized in the model fitting procedures as implemented by SAS PROC LOGISTIC. Wald tests of the model effects will be performed to assess statistical significance; see SAS documentation for details. See Hosmer and Lemeshow, 2000 ⁽⁴⁴⁾ for a discussion of such techniques. Alternative parametric models will be considered if model fit is found to be inadequate.

Objectives based on continuous outcomes such as immune response measured over time will be address in a similar fashion. A series of exploratory analyses will initially take place including individual subject-level profile plots and overall mean plots used to examining the mean structure. Formal statistical examination of longitudinal patterns will be done through the use of

a mixed model. Restricted maximum likelihood estimation will be utilized in the model fitting procedures as implemented by SAS PROC MIXED (version 9.2). Once the model is fit, specific linear contrasts based on the estimated model parameters will be constructed and used to test hypotheses concerning between time point comparisons. We acknowledge the possibility of informative missingness, that is, the probability of a particular observation being missing may be related to the health of the subject, and therefore analyses will be interpreted with caution.

All tests will be two-sided and tested at a 0.05 nominal significance level. Standard diagnostic plots will be used to assess model fit and transformations of variables may be considered in order to meet statistical assumptions.

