12.8 Adverse Event

AEs will be coded using the latest available version of the Medical Dictionary for Regulatory Activities (MedDRA). AEs will be summarized for each treatment arm by the number and percentage of patients who experienced the event, according to system organ class and preferred term. Additional summaries will also be provided by severity grade and relationship to study drug, and for SAEs and events resulting in the permanent discontinuation of therapy. A patient reporting multiple cases of the same AE will be counted once within each system organ class and similarly counted once within each preferred term, and adverse events will be graded by worst severity grade. Unless specified otherwise, the denominator for these calculations will be based on the number of patients in each treatment arm who receive at least one dose of study drug, irrespective of the total number of doses administered. All participants who receive any study treatment will be considered evaluable for toxicity.

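### The toxicity endpoint and its confidence interval stop at Grade 4, so a patient whose only severe toxicity is fatal is not counted

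*Combined protocol and SAP*

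**What the plan says.** Safety and tolerability is a secondary objective (Sections 3.2 and 12.2). Section 12.3 lists its endpoint as the "Number of Grade 3 or 4 toxicities", graded by CTCAE Version 4.

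The Secondary Analyses text in Section 12.7 carries the same limit into the analysis. It names a "toxicity rate (Grade 3 or Grade 4 toxicities, according to National Cancer Institute Common Toxicity Criteria" and says that this rate, together with the objective response rate, "will be estimated using simple relative frequencies". On precision it adds: "The corresponding 95% confidence intervals for the estimated probabilities will be computed using the method proposed", and it cites the Clopper-Pearson paper.

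The severity table in 10.1.2.1 runs from Grade 1 to Grade 5, and for injection site reaction, acneiform rash and induration its Grade 5 entry is death. Grade 5 is therefore a category of its own in this protocol and not part of Grade 4.

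Section 12.8 covers the adverse event summaries. There, "adverse events will be graded by worst severity grade", and tables are planned by severity grade, by relationship to study drug and for serious events. On the population it states: "All participants who receive any study treatment will be considered evaluable for toxicity".

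**The concern.** A severe-toxicity rate should move in the unfavourable direction when the worst toxicity occurs. As worded, this one does not. A fatal toxicity is neither Grade 3 nor Grade 4, so a patient with no other severe toxicity counts in the denominator and not in the numerator.

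The rate is the only safety quantity with a planned confidence interval; Sections 12.6 and 12.8 provide descriptive summaries, counts and percentages. Section 12.1 says that the analyses are meant to give estimates for planning larger comparative trials, so the figure may be carried forward by readers who take it to mean severe toxicity of any kind. Section 12.7 also plans exploratory logistic regression for binary outcomes. If toxicity is modelled with the stated definition, a patient with only a fatal toxicity is coded as having had none.

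**Working it through.** The documents state no toxicity rate, threshold or expected count, so there is no figure to reproduce. The check compares definitions and then illustrates the effect with assumed counts.

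**Definitions side by side**

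- Endpoint (12.3): Grades 3 and 4.
- Rate and interval (12.7): Grades 3 and 4.
- Grading scale (10.1.2.1): Grades 1 to 5, with death as Grade 5.
- Denominator (12.8): everyone who receives any study treatment.
- Any text adding Grade 5 to the endpoint or the rate: none.

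**Size of the gap**

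Let N be the number of treated patients, a the number with at least one Grade 3 or 4 toxicity, and k the number with a Grade 5 toxicity and no Grade 3 or 4 toxicity.

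- Rate as written: a/N.
- Rate with Grade 5 included: (a + k)/N.
- Shortfall: k/N.

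Section 12.1 gives a target of at least 50 evaluable patients and a cap of 65 enrolled, so I use N = 50 and N = 65. For k = 1 the shortfall is 1/50 = 2.0 points or 1/65 = 1.5 points.

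The Clopper-Pearson 95% limits for x out of N are the 2.5% quantile of Beta(x, N − x + 1) and the 97.5% quantile of Beta(x + 1, N − x). For x = 0 the lower limit is 0 and the upper is 1 − 0.025^(1/N), which is 7.1% at N = 50 and 5.5% at N = 65.

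| N | a (assumed) | k (assumed) | As written (95% CI) | Grade 3 or higher (95% CI) |
|---|---|---|---|---|
| 50 | 0 | 1 | 0/50 = 0% (0 to 7.1) | 1/50 = 2.0% (0.05 to 10.6) |
| 50 | 5 | 1 | 5/50 = 10.0% (3.3 to 21.8) | 6/50 = 12.0% (4.5 to 24.3) |
| 65 | 0 | 1 | 0/65 = 0% (0 to 5.5) | 1/65 = 1.5% (0.04 to 8.3) |
| 65 | 10 | 2 | 10/65 = 15.4% (7.6 to 26.5) | 12/65 = 18.5% (9.9 to 30.0) |

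The intervals overlap heavily in every row. The shift is small against the sampling error of a trial this size. What changes is what the estimate means.

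**The case against.** The strongest reply is that little is lost. Section 12.8 already plans summaries by grade, by relationship and for serious events, with all treated patients as the denominator, so a fatal event would show there as Grade 5. Death is a criterion for a serious adverse event (10.2.1), and it counts in PFS and OS. No stopping rule, sample size or test uses the toxicity rate (12.4, 12.10). A rate labelled Grade 3 or 4 is also a correct report of Grades 3 and 4; it is incomplete as a measure of severe toxicity, not miscalculated. All of this stands, and it limits the point to one descriptive endpoint and its interval. It does not remove the gap, because none of those other outputs has an interval.

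Four stronger readings are tempting, and the documents do not support them.

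- *A Grade 4 event that ends in death is reclassified and leaves the numerator.* The worst-grade rule is in Section 12.8 and is written for the adverse event summaries. Sections 12.3 and 12.7 neither contain nor cite it. Applying it to the rate is a reasonable inference but not a stated rule. The gap does not depend on it, since a toxicity that is fatal from the outset never has Grade 3 or 4.
- *Every fatal toxicity drops out.* In a per-patient rate, someone who also had a separate Grade 3 or 4 toxicity is still counted. Section 1.4.4 lists four Grade 3 to 4 haematologic abnormalities, each at 10% incidence or more under temozolomide, so some overlap is plausible and the rows with a = 0 are extreme cases.
- *Table 4 loses fatal events because it stops at Grade 4.* That table, headed "Guidelines for Routine Adverse Event Reporting for Phase 2 Studies", governs routine reporting. Deaths go through the serious adverse event route (10.2), and Section 15.1 puts serious events on both the adverse event page and the serious event form.
- *Correcting the definition can only leave the figure equal or raise it slightly.* That the figure cannot fall is true only of a per-patient rate. Section 12.3 speaks of a number of toxicities and Section 12.7 of a rate, so the unit is not settled. The size of any rise depends on whether deaths not attributed to treatment are counted, and neither section states an attribution rule.

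**Conclusion.** The point holds within these limits. The toxicity endpoint and its Clopper-Pearson rate exclude Grade 5 by their own wording, so a patient whose only severe toxicity is fatal is not counted in the single safety estimate with a planned interval. Each such patient lowers the reported rate by 2.0 points at N = 50 or 1.5 points at N = 65, relative to a rate of Grade 3 or higher.

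This assumes a per-patient rate among treated patients and no other Grade 3 or 4 toxicity in the patient concerned. The event counts are assumed throughout. N = 65 is the enrolment cap, so it is an upper bound on the number treated. Fatal toxicity may prove rare: Section 2 reports no serious adverse event attributable to the vaccine in phase I, although that trial had nine patients (1.8.2). The primary analysis, the sample size and the reporting of deaths elsewhere are unaffected.

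**What to change.** In Sections 12.3 and 12.7, define the toxicity rate as the proportion of treated patients with at least one toxicity of Grade 3 or higher (Grades 3, 4 and 5), and keep the Clopper-Pearson interval. This also settles the unit as patients in both sections.

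In the same sentence, state the attribution rule, using the relationship categories in 10.1.2, and apply it to Grade 5 exactly as to Grades 3 and 4. Without it, deaths from tumour progression within the adverse event window could enter a toxicity rate.

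The cost is a wording change. The grades, relationship and serious event data are already collected, and Table 4 needs no change. The per-patient rate may be slightly higher than under the present wording. The by-grade summaries in Section 12.8 will still show Grades 3, 4 and 5 separately for anyone who needs the narrower figure.

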12.4 Sample Size Determination

The primary endpoint will be the 6 month PFS survival fraction. Let π represent the 6 month PFS survival fraction. A true rate of the 6 month PFS survival fraction greater than π_0 =0.55 is considered acceptable and evidence such that we will the treatment worthy of further study. The null and alternative hypotheses to be tested are H_0 : π = π_0 versus H_a : π > π_0 . We hypothesize that patients treated with SurVaxM and adjuvant temozolomide will have a 6 month PFS survival fraction of 0.70 or larger. The sample size calculation is based on testing the hypotheses concerning the proportion of the population with a response to the treatment: H_0 : π = π_0 versus H_a : π > π_0 . For our calculations π_0 =0.55, α =0.10, 1- β =0.80. Based on an exact one-sided test the sample size calculation yields n=50 patients.

Subjects will be accrued to the study on a first-come basis. The projected accrual is approximately 2 subjects per month, and therefore recruitment is expected to be complete at 25 months following the study starting point. Subjects will be followed to determine time to tumor progression (PFS) and until death to determine overall survival (OS).

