12 STATISTICAL METHODOLOGY

12.1 Study Design

This is a multi-center, open-label; prospective one-arm phase II clinical trial evaluating the safety and efficacy of SurVaxM and adjuvant temozolomide in adult patients with newly diagnosed GBM. The statistical design is based on an assessment of the efficacy of the study treatment for patients as compared to an external standard, i.e., historical control. All enrolled patients will receive the study treatment and initiation of the treatment should take place as soon as possible following study enrollment. A total of up to 65 patients will be enrolled to meet our target of at least 50 evaluable patients. An evaluable subject is defined as a subject who meets eligibility requirements and who completes the initial four priming doses of the vaccine. If a patient signs an Informed Consent and does not receive all four priming injections or, the patient withdraws their consent before receiving the priming injections, the patient will be classified as unevaluable and will be replaced. Analyses will be performed with a focus on estimation of specific clinically important parameters for use in the planning of larger subsequent comparative trials designed to fully assess efficacy and safety.

All analyses will be performed using the SAS® statistical software system.

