12.7 Efficacy Analysis

12.7.1 Primary Analysis

The primary objective is to evaluate the 6 month PFS survival fraction in patients with newly diagnosed GBM treated with at least 4 priming doses of SurVaxM and standard-of-care adjuvant

temozolomide as compared to historical control. PFS is defined as the time from date of diagnosis to the date of first observed disease progression or death due to any cause. Patients who are alive and disease free at the last study assessment will be treated as censored.

Historical Control: Patients in this population defined by the eligibility criteria receive standard-of-care which consists of concurrent temozolomide and radiation followed by adjuvant temozolomide. Based on provided historical information, the 6 month PFS survival fraction is assumed to be 0.55. We hypothesize that treatment with SurVaxM and adjuvant temozolomide will increase the 6 month PFS survival fraction to 0.70. Therefore the PFS survival fraction will be measured after all patients have been followed for 6 months.

The 6 month PFS survival fraction is estimated as standard binomial proportion. An exact one-sided binomial test will be used to test our primary hypothisis. The nominal significance level to be used for this test is 0.10. In addition, a Kaplan-Meier curve for PFS will be used calculated to generate summary descriptive statistics, e.g. median PFS.

Secondary Analyses

The estimated distributions of overall survival (OS), defined as the time from date of diagnosis to death due to any cause, will be obtained using the Kaplan-Meier method. Estimates of quantities such as median survival will be obtained. Corresponding confidence intervals will be computed. It is assumed *a priori* that any drop out times will be non-informative in terms of the censoring mechanism. Groups defined by levels of categorical or dichotomized numeric demographic/baseline variables will be compared in regards to time-to-event distributions using the log-rank test. Cox proportional hazards model regression will be utilized for multivariate analyses.

A summary of anticancer therapies received following the discontinuation of protocol therapy will be provided. Such therapies will be classified as chemotherapy, biological therapy, radiation, surgery, or other.

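### Section 12.4 says an exact one-sided test gives n=50 for alpha 0.10 and power 0.80, but at n=50 no cutoff meets both: the lowest cutoff that holds alpha, 33, has power 0.782

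*Combined protocol and SAP*

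**What the plan says.** Section 12.4 (Sample Size Determination) sets out the inputs: "For our calculations π_0 =0.55, α =0.10, 1- β =0.80". The hypothesis there is that treated patients "will have a 6 month PFS survival fraction of 0.70 or larger". The section concludes: "Based on an exact one-sided test the sample size calculation yields n=50 patients".

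Section 12.7.1 (Primary Analysis) plans the matching test. It says "An exact one-sided binomial test will be used to test our primary hypothisis" and "The nominal significance level to be used for this test is 0.10", estimates the endpoint as a simple binomial proportion, and gives the alternative as a single value: "We hypothesize that treatment with SurVaxM and adjuvant temozolomide will increase the 6 month PFS survival fraction to 0.70".

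Section 12.1 (Study Design) treats 50 as a minimum: "A total of up to 65 patients will be enrolled to meet our target of at least 50 evaluable patients".

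None of these sections, nor the synopsis, gives the number of successes needed to reject, the attained alpha or the attained power.

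**The concern.** With the null, alternative, level, power, sidedness and test all given, an exact calculation can be checked without further assumptions. A binomial count takes whole values only, so the attained alpha and power move in steps and not every sample size can meet a given pair of limits. The plan says that 50 does. If it does not, the only power statement for the primary endpoint is wrong as written.

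There is also a practical side. Someone who trusts the 80% figure and works back to a cutoff could settle on 32 of 50, because that cutoff has power above 0.80 and 33 does not. Yet 32 of 50 is not significant at 0.10 under the planned test.

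**Working it through.** **Inputs.** π0 = 0.55, α = 0.10 and power = 0.80 (section 12.4). π1 = 0.70 (sections 12.4 and 12.7.1). Exact one-sided binomial test (both sections). n = 50 (section 12.4).

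**Formula.** Reject when the number progression-free at 6 months, X, is at least r.

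- Attained alpha = P(X ≥ r | n, 0.55) = Σ C(n,k) · 0.55^k · 0.45^(n−k), for k = r to n.
- Power = P(X ≥ r | n, 0.70) = Σ C(n,k) · 0.70^k · 0.30^(n−k), for k = r to n.

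**Step 1: the plan's own n = 50.**

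| Cutoff r | Observed rate | Attained alpha | Power at 0.70 | Meets both limits? |
|---|---|---|---|---|
| 31 | 62% | 0.1974 | 0.9152 | No, alpha too high |
| 32 | 64% | 0.1273 | 0.8594 | No, alpha too high |
| 33 | 66% | 0.0765 | 0.7822 | No, power too low |
| 34 | 68% | 0.0427 | 0.6839 | No, power too low |

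Lower cutoffs have still larger alpha, and higher cutoffs still less power. The best rule that holds alpha is therefore 33 of 50, with type II error 1 − 0.7822 = 0.2178 against the planned 0.20. The shortfall in power is 0.80 − 0.7822 = 0.0178. A mid-p version does not rescue 32: its mid-p value is 0.1019, still above 0.10.

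**Step 2: search over n.** For each n, take the smallest r with alpha ≤ 0.10.

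| n | r | Alpha | Power at 0.70 |
|---|---|---|---|
| 48 | 32 | 0.0683 | 0.7495 |
| 49 | 32 | 0.0948 | 0.8100 |
| 50 | 33 | 0.0765 | 0.7822 |
| 51 | 34 | 0.0613 | 0.7527 |
| 52 | 34 | 0.0850 | 0.8112 |
| 53 | 35 | 0.0687 | 0.7844 |
| 54 | 35 | 0.0938 | 0.8368 |
| 55 | 36 | 0.0764 | 0.8125 |
| 56 | 37 | 0.0617 | 0.7866 |
| 57 | 37 | 0.0843 | 0.8374 |

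The first size that meets both limits is 49, then 52, 54, 55 and 57. From 57 to 65, every size meets both. 50 is not a solution.

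**Step 3: where 50 might come from.** Two normal approximations round up to 50:

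- Null variance only: (1.2816 + 0.8416)² × 0.55 × 0.45 / 0.15² = 49.6.
- Both variances with a continuity correction: the uncorrected size is 46.53, and (46.53/4) × [1 + √(1 + 1/(46.53 × 0.15))]² = 49.8.

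The documents do not say how 50 was obtained. Rounding 49 up is equally possible, so nothing here depends on the explanation.

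**Step 4: how far off.** The 33-of-50 rule reaches power 0.80 at a true fraction of 0.7039, almost exactly the design value of 0.70.

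**The case against.** The case against concedes the arithmetic and argues that it does not matter.

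- **50 is within a patient or two of an exact solution, and the synopsis calls the sample size approximate.** This is true, and it is why the point is minor. Section 12.4, however, does not claim approximate power. It attributes n = 50 to an exact test at stated limits.
- **50 is a minimum.** Up to 65 may be enrolled, and of the 16 possible sizes from 50 to 65, 12 reach power 0.80. Only 50, 51, 53 and 56 fall short (0.753 to 0.787). This stands as context: the 0.218 type II error applies if exactly 50 are analysed. But 50 is the planned number and the one the power statement covers.
- **Section 12.4 words the alternative as 0.70 or larger, and 0.704 would be enough.** Power has to be stated at a definite value. The lower end of that range is the design value, and section 12.7.1 gives 0.70 outright.
- **The test, level and null already fix the rejection region, so no cutoff need be printed.** This is fair: the missing cutoff is not in itself an error. Printing it is simply the clearest way to correct the power statement.
- **A clause for more than 50 evaluable patients goes beyond the error.** It adds a sentence about the analysed number, but it only applies the exact test that section 12.7.1 already plans.

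**Conclusion.** The statement in section 12.4 is wrong as written. With exactly 50 evaluable patients and a true 6-month PFS fraction of 0.70, the planned test has power 0.782, not 0.80. The size is minor: 1.8 percentage points, due to binomial discreteness. Type I error is not inflated. The attained 0.077 lies below the nominal 0.10, as is usual for an exact test. The finding does not show that the trial is materially underpowered, and it gives no reason to change the target of 50. It rests only on figures stated in the plan, with each evaluable patient counted as a success or a failure in a binomial proportion, as section 12.7.1 provides.

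**What to change.** Keep the target of 50 evaluable patients and replace the power statement in section 12.4 with:

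> With 50 evaluable patients, H0 is rejected if at least 33 are progression-free at 6 months (exact one-sided alpha 0.077; power 0.78 at a true rate of 0.70); if more than 50 are evaluable, all are analysed with the exact cutoff for that n.

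The last clause is needed because the cutoff moves with the number analysed: it is 33 at n = 50, 34 at 51 and 52, and 35 at 53.

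The cost is one sentence and a slightly less favourable stated power. The sample size, replacement places, test and nominal alpha do not change.
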